6.2.2 Visit 1/Baseline (Day 1)

The following procedures must be performed and recorded at the Baseline visit. If Screening and Baseline visits occur the same day, procedures with an asterisk (*) should only be performed once and will be recorded as Baseline values.

1. Complete age-matched Dermatology Life Quality Index (DLQI) assessment, as applicable.
2. Perform a brief physical examination.
3. Perform lesion mapping and lesion count.*
4. Perform BOTE Inflammation Score (pre-dose).
5. Obtain urine pregnancy test, as applicable. If pregnancy test is positive, the subject may not participate in the study.
6. Update concomitant medication information.

7. Confirm eligibility and randomize subject.
8. Dispense subject diary and study drug.
9. Weigh and record study product tubes.
10. Instruct subject on dispensing, mixing, and application of study product and diary completion.
11. Have subject/caregiver apply first dose in clinic from kit assigned at randomization.
12. Complete Local Skin Reaction assessment approximately 30 minutes post dose.
13. Collect and record AE information for any AEs reported.

6.2.3 *Visit 2/Day 2 Telephone Contact*

The following procedure must be performed and recorded at the Day 2 telephone contact.

1. Contact subject to confirm how the subject is feeling.

6.2.4 *Visit 3/Week 2 (Day 15 ±3)*

The following procedures must be performed and recorded at the Week 2 visit.

1. Perform lesion mapping and update lesion map with location for any new lesions.
2. Assess for subject recurrence of MC.
3. Review study compliance.
4. Dispense subject diary.
5. Review dosing instructions and have subject/caregiver apply daily dose in clinic using the kit assigned at randomization.
6. Perform BOTE Inflammation Score (post-dose).
7. Complete Local Skin Reaction Assessment (post-dose).
8. Collect and record AE information for AEs reported.
9. Update concomitant medication information and confirm if any new occurrences of MC were reported in the subject's household.

6.2.5 Visit 4/Week 4 (Day 29 ±5)

The following procedures must be performed and recorded at the Week 4 visit.

1. Obtain pregnancy test and evaluate results, as applicable. If pregnancy test is positive, the subject may continue in the study; however, study drug should be discontinued.
2. Perform lesion counts and update lesion map with location for any new lesions.
3. Assess for subject recurrence of MC.
4. Perform scarring/keloid assessment.
5. Weigh returned study drug and review study compliance.
6. Weigh, record, and dispense new supply of study product and dispense subject diary.
7. Review dosing instructions and have subject/caregiver apply daily dose in clinic using the newly dispensed kit.
8. Perform BOTE Inflammation Score (post-dose).
9. Perform Local Skin Reaction Assessment (post-dose).
10. Collect and record AE information for AEs reported.
11. Update concomitant medication information and confirm if any new occurrences of MC were reported in the subject's household.

6.2.6 Visit 5/Week 8 (Day 57 ±5)

The following procedures must be performed and recorded at the Week 8 visit.

1. Obtain pregnancy test and evaluate results, as applicable. If pregnancy test is positive, the subject may continue in the study; however, study drug should be discontinued.
2. Perform lesion mapping and update lesion map with location for any new lesions.
3. Perform scarring/keloid assessment.
4. Weigh returned study drug and review study compliance.
5. Weigh, record, and dispense new supply of study product and dispense subject diary.

6. Review dosing instructions and have subject/caregiver apply daily dose in clinic using the newly dispensed kit.
7. Perform BOTE Inflammation Score (post-dose).
8. Perform Local Skin Reaction Assessment (post-dose).
9. Collect and record AE information for AEs reported.
10. Update concomitant medication information and confirm if any new occurrences of MC were reported in the subject's household.

6.2.7 *Visit 6/Week 12/ET (Day 85 ±5)*

The following procedures must be performed and recorded at the Week 12/ET1 visit.

1. Complete age-matched Dermatology Life Quality Index (DLQI) assessment, as applicable.
2. Obtain pregnancy test and evaluate results, as applicable.
3. Perform lesion mapping and update lesion map with location for any new lesions.
4. Perform scarring/keloid assessment
5. Perform a brief physical examination.
6. Subject/caregiver administer final dose of study drug from previously dispensed kit.
7. Perform BOTE Inflammation Score (post-dose).
8. Perform Local Skin Reaction Assessment (post-dose).
9. Weigh returned study drug and review study compliance.
10. Collect and record AE information for AEs reported.
11. Update concomitant medication information and confirm if any new occurrences of MC were reported in the subject's household.

6.2.8 *Visit 7/Week 16 and Visit 8/Week 20 (Day 113 +/- 7 days; Day 141 +/- 7 days)*

The following procedures must be performed and recorded at the Week 16 and Week 20 visits. It is expected that these visits should be done by telephone.

1. Collect and record information for new and ongoing AEs, including recurrence of MC.
2. Update concomitant medication information.

6.2.9 *Visit 9/Week 24 (Day 169 +/- 7 days)*

The following procedures must be performed and recorded at the Week 24 visit.

1. Perform scarring/keloid assessment.
2. Collect and record information for new and ongoing AEs, including subject recurrence of MC.
3. Update concomitant medication information.

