6.3 Discontinuation

6.3.1 *Treatment Discontinuation*

If at any time during the study the investigator determines that it is not in the best interest of the subject to continue treatment, the subject's treatment will be discontinued. The investigator can discontinue the treatment for a subject at any time if medically necessary. If a subject's treatment is permanently discontinued by the investigator because of an AE, that AE should be indicated as the reason for treatment discontinuation. In this case, the subject is discontinued from the treatment, but still participates in the study and the subject is encouraged to follow the visit schedule and complete all assessments.

In addition, the investigator may instruct the subject to temporarily halt treatment of a specified region (i.e., due to an adverse event). This treatment modification and the reason for the temporary drug interruption should be documented in the subject's source documents and eCRF. The lesions in the impacted area should continue to be counted in the lesion count during the period of treatment modification.

The investigator may discontinue a subject's treatment if the subject/caregiver has failed to follow study procedures or to keep follow-up appointments. Appropriate documentation in the subject's study record and the study database regarding the reason for treatment discontinuation must be completed.

Reasons for an investigator's withdrawal of a subject **from the treatment** may include, but are not limited to, the following:

- Safety (e.g., severe adverse reactions, pregnancy)

- When a concomitant medication or treatment likely to interfere with the results of the study is reported, or required, by the subject, the investigator will decide, in consultation with the CRO whether the subject is to be withdrawn.

Reason(s) for discontinuation from the treatment as listed in the study record will be entered into the study database as follows:

- Completed (complete clearance prior to Week 12)
- Adverse Event (including LSRs deemed to be significant by investigator)
- Withdrawal by Subject/Caregiver
- Physician Decision
- Protocol Violation
- Lost to Follow-Up
- Pregnancy
- Lack of Efficacy
- Worsening of Molluscum Contagiosum
- Other

6.3.2 *Study Discontinuation*

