8.5 Dose and Administration

Subjects will apply treatment once daily for up to 12 weeks to all active lesions identified at baseline and new lesions that arise during treatment. If the investigator determines all lesions are cleared at a clinic visit, the treatment may stop. If treatment is stopped due to clearance, subjects will continue regularly scheduled visits through Week 24/ET2.

An increase in the number of MC lesions (with or without inflammatory reaction) during the early treatment phase is often observed. It is important to instruct the subject/caregiver to treat the new lesions as well as the existing lesions.

Each dose will consist of berdazimer gel or vehicle gel with hydrogel thoroughly mixed together by the subject or caregiver and applied to the lesions and approximately 1 cm surrounding each lesion. Periocular lesions will be treated if the lesions are at least 2 cm from the edge of the eye. If a subject has more than 20 MC, a second dose of berdazimer gel or vehicle gel with hydrogel can be prepared to ensure appropriate coverage of all lesions.

At the investigator's discretion, the subject may be placed on a drug holiday for up to 2 weeks at a time in the event of a significant local skin reaction (LSR). This will be captured in the electronic data capture (EDC) system and the subject's diary. The investigator should instruct the subject how long to hold study drug and the planned date to re-start treatment. Site staff should contact the subject on the day of the planned re-start and assess whether the LSR has resolved enough to resume treatment. If it has not resolved sufficiently, the drug holiday may be extended as long as the entire extension has not exceeded 2 weeks. If the LSR flares after re-introduction of study drug, the study drug should be permanently discontinued and the EDC system updated appropriately. Please see [Section 7.2.4](#) for additional information.

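### Table 1 footnote 6 drops the Week 12 clinic dose that four other places require or presume, and the Week 12/ET1 dose step has no on-treatment condition

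*Combined protocol and SAP*

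**What the plan says.** **Week 12 dosing.** Section 6.2.7 opens with "The following procedures must be performed and recorded at the Week 12/ET1 visit". Its item 6 reads "Subject/caregiver administer final dose of study drug from previously dispensed kit", and items 7 and 8 are the BOTE and LSR scores, both labelled post-dose. Section 6.1 names Week 12 among the visits with clinic application. The in-clinic application row of Table 1 is marked at Visit 6 (Week 12/ET1), and Table 1 footnote 4 has BOTE scored after dosing up to Visit 6. Footnote 6, which annotates that same row, stops clinic application at Visit 5 (Week 8) and adds that subjects do not dose at home on a visit day.

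**Stops and holds.** Under section 6.3.1, after an investigator's permanent stop for an adverse event, "the subject is discontinued from the treatment, but still participates in the study and the subject is encouraged to follow the visit schedule". Section 8.5 says "If the LSR flares after re-introduction of study drug, the study drug should be permanently discontinued and the EDC system updated appropriately", and for a significant LSR it allows that "the subject may be placed on a drug holiday for up to 2 weeks at a time". Sections 7.2.4 and 7.2.5 say that suspected allergic contact dermatitis should lead to permanent discontinuation, that the Week 12/ET1 assessments should be done at that moment, and that the subject should then stay in the study to Week 24.

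**Earlier visits.** The Week 2 list has "Review dosing instructions and have subject/caregiver apply daily dose in clinic using the kit assigned at randomization". The Week 4 and Week 8 lists have "Review dosing instructions and have subject/caregiver apply daily dose in clinic using the newly dispensed kit". None of these steps carries a condition either.

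**The concern.** Two site instructions do not fit the rest of the protocol.

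The first is footnote 6. Sites work from the schedule table. A site that reads the footnote gives no Week 12 dose, and a site that reads the row mark or section 6.2.7 does give one. Both then complete BOTE and LSR items labelled post-dose. The final SAP tabulates LSR component scores at each scheduled post-baseline assessment (section 13.2) and shifts BOTE from baseline to each such assessment (section 12). Week 12 columns could therefore combine scores taken after a fresh application with scores taken on a day without one, with nothing in the label to tell them apart.

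The second is the unconditional dose in the Week 12/ET1 list. That list is invoked at the point when drug is being stopped for a suspected sensitisation. Followed literally, it would re-expose the subject. The population includes children from 6 months of age.

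**Working it through.** No power, alpha or sample-size figure is involved. The check is a comparison of the text.

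**Step 1: is there a Week 12 clinic dose?**

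| Place | Week 12 (Visit 6) clinic dose |
|---|---|
| Table 1, in-clinic application row | Yes: marked at Visits 1, 3, 4, 5 and 6 |
| Table 1, footnote 4 | Presumed: BOTE post-dose from Visit 3 to Visit 6; LSR post-dose at each applicable visit |
| Section 6.1 | Yes: Week 12 is named |
| Section 6.2.7, item 6 | Yes: final dose listed |
| Table 1, footnote 6 | No: ends at Visit 5 |

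The row marks 5 dosing visits. Footnote 6 covers 4 clinic visits (1, 3, 4 and 5). 5 − 4 = 1, so the footnote is one visit short, and it stands alone against four other places.

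**Step 2: could the dose simply move to the home?** No. Footnote 6 excludes home application on visit days, and section 1.2.1 says the visit-day dose is applied in clinic. Read literally, footnote 6 leaves no dose at all on the day of the Week 12 visit.

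**Step 3: what is scored after it?** In section 6.2.7 the order is lesion mapping (item 3), dose (item 6), BOTE (item 7), LSR (item 8). The two skin scores follow the disputed dose. Lesion mapping comes before it, so whether the dose is given cannot change that visit's lesion assessment or the primary endpoint.

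**Step 4: the suspected contact dermatitis path.**

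1. Sections 7.2.4 and 7.2.5: drug should stop permanently.
2. Same sections: the Week 12/ET1 assessments should be done at that time.
3. Section 6.2.7: the procedures at that visit must be performed. Item 6 is a dose, and items 7 and 8 are assessments described as following a dose.
4. Sections 7.2.4 and 7.2.5: the subject then continues to Week 24, so can meet the same list again at the scheduled Week 12 visit.

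Nothing in item 6 limits it to subjects still on drug. Elsewhere in the same list the authors did qualify items: the quality-of-life questionnaire and the pregnancy test are to be done only where applicable.

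**Step 5: the other lists.** The dose step is unconditional in sections 6.2.4 (item 5), 6.2.5 (item 7), 6.2.6 (item 6) and 6.2.7 (item 6), that is, 4 of 4 post-baseline treatment-period clinic lists. The first three refer to the daily dose; only 6.2.7 refers to a final dose.

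**Step 6: how often?** This cannot be estimated from the documents. The nearest figure is from Phase 2: no subject on 12% once daily stopped treatment for an adverse event (section 1.2.2), out of 48 (section 1.1).

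**The case against.** The strongest reply is that the visit lists have to be read with the rest of the protocol. Section 1.2.1 shows that the clinic step fixes where that day's dose is taken; it does not add a dose. A subject who is stopped or on hold has no daily dose due. The lists already operate under stop rules: at Weeks 4 and 8 the pregnancy item says "If pregnancy test is positive, the subject may continue in the study; however, study drug should be discontinued", yet the later dose step is unqualified, and nobody would read it as cancelling the stop. A wholly literal reading would also have sites dispense new drug to permanently stopped subjects. During a drug holiday, section 4.1 explains that drug is still handed out so that dosing can resume before the next visit, and sections 7.2.4 and 8.5 have staff contact the subject on the planned restart day.

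Most of this stands. A reader might infer that all four lists oblige sites to dose subjects who are off drug. The documents do not support that, because the specific stop and hold rules in sections 4.1, 6.3.1, 7.2.4, 8.5 and 9.5 govern.

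The reply does not dispose of two things. Footnote 6 is itself a specific instruction, so letting the specific rule prevail does not settle the contradiction; only the weight of the other four places does. And the daily-dose argument is weakest in section 6.2.7, which speaks of a final dose and is the list called up at a permanent stop. One can say that a dose is not an assessment, but the BOTE and LSR assessments in that list are themselves labelled post-dose.

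**Conclusion.** Wrong as written, and minor. Footnote 6 contradicts four other places, and the likely consequence is inconsistent Week 12 BOTE and LSR scoring between sites. The Week 12/ET1 dose step conflicts on its face with the permanent-stop rule that invokes that list. The rule prevails, and a careful site would not dose, but the list leaves an avoidable risk of re-exposure.

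This rests on reading the Table 1 row as marked at Visit 6, and on some sites following the footnote and others following the list. Neither the number of such sites nor the number of subjects is known.

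Three stronger readings should not be drawn:

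- **Pregnancy.** A reader might infer that a subject with a positive Week 12 test would be dosed, because the stop sentence used at Weeks 4 and 8 is missing there. Section 9.5 requires permanent discontinuation once pregnancy is confirmed and has no visit limit, and the result is evaluated (item 2) before the dose (item 6).
- **Exposure and holds.** A reader might try to put a size on this by counting how often a drug holiday would coincide with a visit, or by how much one stray dose would lengthen recorded treatment. The first counts calendar overlap and the second presupposes the error; neither measures harm.
- **Efficacy.** No effect on the primary endpoint, power or alpha follows, and no direction of bias between arms is claimed.

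**What to change.** 1. Change Table 1 footnote 6 so that clinic application runs *through Visit 6*.
2. Add *only if still on study treatment and not on a drug holiday* to the dose step in section 6.2.7 and, for consistency, to the dose steps in sections 6.2.4, 6.2.5 and 6.2.6.

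Two clarifications are optional: repeat the pregnancy stop sentence beside the Week 12/ET1 test, and label the BOTE and LSR items as post-dose if dosed. The footnote change removes the disagreement between sites. Subjects properly off drug will still be scored without a dose, and the relabelling would make that visible.

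The cost is one footnote and four dose steps, made through a protocol amendment as section 15 requires for a permanent change. There are no added visits, subjects or assessments, and no SAP change.

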6.3 Discontinuation

6.3.1 *Treatment Discontinuation*

If at any time during the study the investigator determines that it is not in the best interest of the subject to continue treatment, the subject's treatment will be discontinued. The investigator can discontinue the treatment for a subject at any time if medically necessary. If a subject's treatment is permanently discontinued by the investigator because of an AE, that AE should be indicated as the reason for treatment discontinuation. In this case, the subject is discontinued from the treatment, but still participates in the study and the subject is encouraged to follow the visit schedule and complete all assessments.

In addition, the investigator may instruct the subject to temporarily halt treatment of a specified region (i.e., due to an adverse event). This treatment modification and the reason for the temporary drug interruption should be documented in the subject's source documents and eCRF. The lesions in the impacted area should continue to be counted in the lesion count during the period of treatment modification.

The investigator may discontinue a subject's treatment if the subject/caregiver has failed to follow study procedures or to keep follow-up appointments. Appropriate documentation in the subject's study record and the study database regarding the reason for treatment discontinuation must be completed.

Reasons for an investigator's withdrawal of a subject **from the treatment** may include, but are not limited to, the following:

- Safety (e.g., severe adverse reactions, pregnancy)

- When a concomitant medication or treatment likely to interfere with the results of the study is reported, or required, by the subject, the investigator will decide, in consultation with the CRO whether the subject is to be withdrawn.

Reason(s) for discontinuation from the treatment as listed in the study record will be entered into the study database as follows:

- Completed (complete clearance prior to Week 12)
- Adverse Event (including LSRs deemed to be significant by investigator)
- Withdrawal by Subject/Caregiver
- Physician Decision
- Protocol Violation
- Lost to Follow-Up
- Pregnancy
- Lack of Efficacy
- Worsening of Molluscum Contagiosum
- Other

6.3.2 *Study Discontinuation*

A subject/caregiver may voluntarily withdraw from study participation at any time. If the subject/caregiver withdraws consent and discontinues from the study, the investigator will attempt to determine the reason for discontinuation and record the reason in the subject's study records and in the study database. In the event of discontinuation from the study, (i.e., prior to Week 12/ET1) every effort should be made to have the subject return to the study center to complete the Week 12 evaluations (ET1 visit). Subjects who withdraw from the study will not be replaced. Subjects who discontinue from the study after Week 12 but prior to Week 24 will be asked to return to the study center to complete the Week 24 evaluations (ET2 visit).

All subjects who fail to return to the study center will be contacted by telephone to determine the reason(s) why the subject failed to return for the necessary visit or elected to discontinue from the study. If a subject/caregiver is unreachable by telephone after a minimum of two documented attempts (one attempt on two different days), a certified letter will be sent requesting that the

subject contacts the investigator. These actions will be reported on the subject's study record and a copy of the follow-up letter maintained in the investigator's file.

An investigator may withdraw a subject from the study when a subject is lost to follow-up.

All premature discontinuations and their causes must be carefully documented in the subject's study record and in the study database.

All Week 12 or Week 24 evaluations should be performed at the time of premature discontinuation as applicable. All data gathered on the subject prior to termination will be made available to the CRO. The investigative site should make all reasonable efforts to ensure the subject returns to complete the appropriate termination visit, even if the subject is not able to attend other study visits.

Study completion or reason(s) for discontinuation from the study as listed in the study record will be entered into the study database as follows:

- Completed Treatment Per Investigator's Instructions and Completed All Study Visits
- Withdrawal by Subject/Caregiver
- Lost to Follow-Up

Novan has the right to terminate or stop the study at any time. Should this be necessary, the investigator will ensure that proper study discontinuation procedures are completed.

7 DESCRIPTION OF STUDY PROCEDURES

Study procedures and their timings are summarized in the Schedule of Assessments (refer to [Table 1](#)).

7.1 Efficacy Assessments

7.1.1 *Molluscum Contagiosum Lesion Counts*

Molluscum contagiosum is a viral infection characterized by small, discrete, waxy, skin-colored, dome-shaped papules, an average of 3–5 mm in diameter. The papules may be umbilicated and contain a caseous plug. When the lesions are squeezed or traumatized, a creamy, grey-white material can be extruded. If the investigator cannot clearly differentiate the lesions as is the case for agminated (clustered lesions) this should be counted as one lesion. If the investigator can differentiate and count the umbilical tops separately, each lesion should be counted separately. The

investigator should be consistent with the method of recording agminated lesions throughout the study.

For the purpose of this clinical trial, only active MC lesions are counted. Treatable lesions are any active (raised, palpable) MC lesions that are dome-shaped, pearly and shiny white top centered papules that are at least 2 cm away from the ocular region.

All study personnel who will perform lesion counts must pass the study training including lesion count training. Training on how to accurately count the number of MC lesions will be provided.

Mapping of lesions: At every visit from Baseline through Week 12, all lesions should be recorded on the body map and will clearly note the location of each lesion or agminated lesion. The lesion map is intended to assist study personnel in performing lesion counting and scar/keloid assessment.

Definition of Clearance: For the purpose of this study, “clear” means resolution of the active (raised, palpable) treatable molluscum lesion(s). After resolution, the residual surface changes such as pitted scar (indentation) < 1 mm in depth at the molluscum lesion area (<5 mm in diameter), hyper or hypopigmentation may remain. As these are considered part of the normal healing, they will not be captured as adverse events. Refer to the lesion count training for details.

The same evaluator should perform lesion counts at Screening, Baseline, and Weeks 2, 4, 8 and 12/ET1. In the event that this is not possible due to unforeseen circumstances, a different evaluator may evaluate the subject. The evaluator must pass the study training including lesion count training. It is particularly important to ensure the same evaluator performs the Baseline and Week 12/ET1 for lesion count for a subject and also Baseline and Week 24/ET2 assessment for scarring/keloid scarring.

